9.3. Subject Population(s) for Analysis

All randomized and completed study patient data will be used for primary and secondary analysis. Primary analysis include needs for dose adjustment of the Envarsus XR or tacrolimus and secondary analysis include duration of recovery from the DGF.

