5.1.1. Primary Study Endpoints

The primary endpoint of the study will be the interval between first dialysis and last dialysis after kidney transplant (duration of DGF).

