5.1.3. Primary Safety Endpoints

Primary safety endpoints include: infections, malignancies, hematological complications including leukopenia, anemia, and thrombocytopenia, cardiovascular complications and events, neuropathy, tremors, gastrointestinal symptoms, uncontrolled hypertension, serious electrolytes abnormalities and immunosuppression-related adverse effects.

6. Study Subjects – Enrollment and Withdrawal

- A total of 100 subjects (50 subjects in each arm) with the diagnosis of DGF will be enrolled over a period of 2 years.
- DGF is defined as the need for a dialysis within the first week of transplant. Once potential DGF patients are identified, the transplant nephrology team will be consulted and the transplant nephrology provider will perform initial evaluation of a patient, discussion with the patient about his/her interest in participating in the research study and inform the research coordinator.
- Subjects will participate in the study until the recovery of DGF as documented by the provider as “discharged from the DGF clinic” or no need for dialysis for more than one week (7 days).
- Subject would be followed for maximum of 3 months. If they still need dialysis beyond 3 months, will be declared as primary dysfunction and will disqualify from the study.

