6.7.2. When and How to Withdraw Subjects

If patient is unable to tolerate the study drug Envarsus XR or SOC drug tacrolimus, the subject will be withdrawn from the study, and likely be switched to other immunosuppressive medications for example cyclosporine, or belatacept or any other immunosuppressive medications based on the clinical discretion. Subjects that are withdrawn will be asked to return for one last study visit to conduct the procedures described in the last visit in the protocol.

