6.7.3. Data Collection and Follow-up for Withdrawn Subjects

Data for the study purpose will not be collected from subjects who have withdrawn from the study but have active treatment either with SOC tacrolimus or with study drug, Envarsus-XR.

7. Study Agent

Subjects will be randomized to receive (in a 1:1 manner) to either the standard of care arm or the experimental arm:

- Standard of Care: Immediate release tacrolimus
- Experimental: Envarsus XR

This study is exempt from the requirements of an IND based on meeting the criteria defined in the FDA information sheet "[Off-Label and Investigational Use Of Marketed Drugs, Biologics, and Medical Devices](#)".

21 CFR 312.2(b) Exemptions. (1) The clinical investigation of a drug product that is lawfully marketed in the United States is exempt from the requirements of this part if all the following apply:

- (i) The investigation is not intended to be reported to FDA as a well-controlled study in support of a new indication for use nor intended to be used to support any other significant change in the labeling for the drug;
- (ii) If the drug that is undergoing investigation is lawfully marketed as a prescription drug product, the investigation is not intended to support a significant change in the advertising for the product;
- (iii) The investigation does not involve a route of administration or dosage level or use in a patient population or other factor that significantly increases the risks (or decreases the acceptability of the risks) associated with the use of the drug product;
- (iv) The investigation is conducted in compliance with the requirements for institutional review set forth in part 56 and with the requirements for informed consent set forth in part 50; and
- (v) The investigation is conducted in compliance with the requirements of 312.7.

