7.4. Randomization and Blinding of Study Drug

This study will be a randomized, unblinded study involving extended release tacrolimus called Envarsus XR once a day and immediate acting tacrolimus twice a day.

8. Study Procedures

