11.5.1. Subject Stopping Rules

Subjects will be informed that they have the right to withdraw from the study at any time for any reason, without prejudice to their medical care. The investigator also has the right to withdraw patients from the study for any of the following reasons:

- If study drug is discontinued due to AE
- If a subject is withdrawn due to an adverse event, the dose adjustment, modification and withdrawal procedures related to adverse events will be followed and will be switched to other alternative medications..
- Protocol violation
- Lost to follow-up
- Study terminated
- Non-compliance

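### The analysis set is limited to completers while anyone still on dialysis at 3 months is disqualified, so the longest primary-endpoint values can be dropped after randomisation

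*Combined protocol and SAP*

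**What the plan says.** - **Endpoint (5.1.1).** "The primary endpoint of the study will be the interval between first dialysis and last dialysis after kidney transplant (duration of DGF").
- **3-month rule (Section 6, last bullet).** Follow-up stops at 3 months. "If they still need dialysis beyond 3 months, will be declared as primary dysfunction and will disqualify from the study".
- **Analysis set (9.3).** "All randomized and completed study patient data will be used for primary and secondary analysis". Neither 9.3 nor any other section defines completion, names an all-randomised set, or says that disqualified subjects stay in the analysis.
- **Withdrawal (6.7.2, 11.5.1).** "If patient is unable to tolerate the study drug Envarsus XR or SOC drug tacrolimus, the subject will be withdrawn from the study". Separately, "The investigator also has the right to withdraw patients from the study for any of the following reasons"; the list includes adverse events, protocol violation and non-compliance.
- **Data after withdrawal (6.7.2, 6.7.3).** "Subjects that are withdrawn will be asked to return for one last study visit". After that, study data "will not be collected from subjects who have withdrawn from the study but have active treatment either with SOC tacrolimus or with study drug". Subjects switched to another drug are not addressed.
- **Blinding (7.4).** "This study will be a randomized, unblinded study".
- **Methods (9.2, 10.2.4).** Continuous data get a t-test or Wilcoxon test. Kaplan-Meier is mentioned for graft survival only. Missing data lead to a further look at the records; there is no scoring or imputation rule.

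**The concern.** A subject still on dialysis at 3 months has one of the longest possible values of the primary endpoint. Disqualifying that subject and then analysing completers is selection on the outcome after randomisation. Participation otherwise ends at recovery (Section 6, 8.2.3), so the natural reading of a completer is a subject who recovered.

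Only the 3-month rule selects on the outcome itself. Withdrawal for intolerance, adverse events or non-compliance is a second route out. It may depend on treatment, because the arm is known to everyone who decides.

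Death or graft loss before recovery has no score either. Taken literally, the interval stops at the last dialysis session, so an early death counts as short DGF.

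If failures are commoner in one arm, a completer analysis leaves them out and flatters that arm. If the wording stays open, the choice of who counts will be made with unblinded data in hand.

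**Working it through.** **Inputs.** From 9.1: control mean 13.9 days, SD 7, target below 10 days (10 used here), 50 per arm analysed. From Section 6: 100 enrolled, 50 per arm. From 9.2: significance at 0.05. Assumed: two-sided testing, 90 days for a non-recoverer, the numbers of non-recoverers, gamma-distributed durations, and 5 days for an early death or graft loss. The documents give no rate of dialysis beyond 3 months.

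**1. The plan's own figure.** For a difference of 13.9 - 10 = 3.9 days and SD 7, two-sided 5% and an assumed 80% power, the normal-approximation formula gives 51 per arm, against 50 stated. Power at 50 per arm is 78.8% (noncentral t). The sample size therefore reproduces, and the problem lies elsewhere.

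**2. Effect on the mean difference.** With k non-recoverers among 50:

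arm mean = (completer mean x (50 - k) + 90 x k) / 50

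For example, Envarsus XR with k = 2: (10 x 48 + 90 x 2) / 50 = 13.2, and 13.9 - 13.2 = 0.7 days.

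| Non-recoverers, control vs Envarsus XR | Difference, completers (days) | Difference, all randomised (days) |
|---|---|---|
| 0 vs 0 | 3.9 | 3.90 |
| 0 vs 1 | 3.9 | 2.30 |
| 0 vs 2 | 3.9 | 0.70 |
| 0 vs 3 | 3.9 | -0.90 |
| 1 vs 1 | 3.9 | 3.82 |
| 2 vs 2 | 3.9 | 3.74 |

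The excess that erases the effect is 3.9 x 50 / (90 - 10) = 2.4 subjects of 50.

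**3. Effect on the test.** Simulation with 5,000 trials per case; recoverers' durations are gamma with means 13.9 and 10 and SD 7. The table shows the share of trials significant in favour of Envarsus XR.

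| Control vs Envarsus XR | Wilcoxon, completers | Worst-rank Wilcoxon, all randomised |
|---|---|---|
| 0 vs 0 | 89% | 89% |
| 1 vs 1 | 87% | 86% |
| 2 vs 2 | 88% | 85% |
| 3 vs 3 | 86% | 81% |
| 0 vs 1 | 88% | 84% |
| 0 vs 2 | 88% | 77% |
| 0 vs 3 | 87% | 68% |
| 0 vs 5 | 87% | 49% |
| 3 vs 0 | 88% | 95% |

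The completer column hardly moves: that analysis cannot see the failures, whichever arm they fall in.

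**4. Death or graft loss.** One control subject scored literally at 5 days lowers that arm's mean by (13.9 - 5) / 50 = 0.18 days. This is small, but it makes a failure look like a good result.

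**5. Numbers.** Enrolment equals the number to be analysed, so each exclusion costs power. By t-test, power is 78.8% at 50 per arm, 77.1% at 48, 74.3% at 45 and 69.2% at 40.

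**The case against.** **The wording could mean something else.** Section 6 enrols 100 and 9.1 aims to analyse 100, which fits best if everyone is analysed. A subject followed to the 3-month limit could be called complete, and the disqualification sentence is not in the analysis section. This is a fair reading. But nothing in the documents adopts it, and even then the plan gives no value for a subject still on dialysis.

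**The bias can run either way.** If control has the excess, dropping non-recoverers hurts Envarsus XR: 88% for completers against 95% for worst rank at 3 vs 0. This stands; the direction cannot be known in advance.

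**False positives among recoverers do not increase.** With equal recoverer means (13.9 days in both arms) and 0 vs 3 or 0 vs 5 non-recoverers, the completer Wilcoxon favours Envarsus XR in about 2.5% of trials, the nominal rate. This also stands. The damage is that a benefit among recoverers is reported as a benefit of the assigned treatment, and that an excess of failures goes unseen.

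**Large imbalances may be rare.** If 13.9 ± 7 days describes all DGF patients, 90-day values can make up at most about 49 / 76.1² = 0.8% of them. If that figure already leaves out non-recoverers, the rate is unknown. At an equal 2% rate, an Envarsus XR excess of 3 or more arises by chance in about 3.6% of trials. This limits the likely size of the problem but does not remove it.

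**Some of the withdrawal text is softer.** Section 11.5.1 permits withdrawal and does not require it, 6.7.3 does not literally bar data on switched subjects, and 9.2 plans graft survival curves if appropriate. None of this gives the primary endpoint a value for these subjects.

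**Conclusion.** The concern holds. As written, 9.3 and Section 6 allow the longest primary-endpoint values to be removed after randomisation, and no section retains or scores them. The size depends on imbalance. Under the 90-day assumption, an excess of two or three non-recoverers among 50 is enough to remove or reverse a 3.9-day difference, while balanced exclusions leave it almost unchanged. If no subject needs dialysis beyond 3 months, this route has no effect; withdrawal and the scoring of death or graft loss would still be open.

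It should be settled before analysis. It concerns the primary comparison of an unblinded trial, and a rule chosen after the data are seen will not be credible. A separate conflict needs its own correction: 9.3 calls dose adjustment the primary analysis and DGF duration the secondary one, the reverse of 5.1.1 and 5.1.2. The population sentence covers both analyses, so this point is unaffected.

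**What to change.** 1. **9.3.** Define the primary analysis set as all randomised subjects in their assigned arm. Define completers and keep that set as a sensitivity analysis.
2. **Section 6.** For analysis purposes only, replace disqualification with retention as not recovered by 3 months.
3. **9.2.** Make the Wilcoxon rank-sum test primary for DGF duration. Give the worst rank to subjects not recovered by 3 months and to those who die or lose the graft before recovery. A t-test with values capped at 90 days is a poor substitute: one such subject in each arm raises the control SD from 7 to 12.7 and cuts power from 80% to 31% (normal approximation). Time to recovery, censored where follow-up is lost, is an acceptable alternative if death and graft loss count as non-recovery.
4. **6.7.3.** State that dialysis dates, graft status and vital status are extracted to 3 months for every randomised subject, whatever drug they take, unless authorisation is revoked. State how subjects lost to follow-up or with revoked authorisation are handled, since worst rank does not settle those cases.

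**Cost.** Wording in four sections and some extra extraction from the medical record and Transplant Database, which the trial already uses (10.2.1, 10.2.4). No new visits and no change to treatment. The statistical price is some dilution: simulated power is 89% with no non-recoverers, then 86%, 85% and 81% with 1, 2 and 3 in each arm.

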3.2. Hypothesis

With extended release Envarsus XR, designed to deliver tacrolimus more consistently, it is hypothesized that there will be less fluctuation of tacrolimus levels requiring less dose adjustment and ultimately early recovery of the DGF.

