3.5.3. Potential Benefits to the Subjects

It is anticipated that the subject will benefit through early recovery of DGF, with shorter duration of dialysis treatment after transplant. This ultimately will lead to the prolonged graft survival.

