3.5.4. Risk Minimization

Serious Adverse Events (SAEs) will be reviewed to determine if additional risk could be posed to the subject in question or others participating in the study. If it is determined that a serious adverse event, new information, or an unanticipated event could pose a potential risk to subjects, the DMC and/or the investigator may decide to stop the study.

4. Study Objectives and Purpose

- Primary Objective: Early recovery from DGF
- Secondary Objective: To assess the efficacy of Envarsus XR in kidney transplant recipients with DGF in achieving steady state tacrolimus levels compared to immediate release tacrolimus administration (SOC).

5. Study Design and Endpoints

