5.1.2. Secondary Study Endpoints

The secondary endpoint will be number of tacrolimus or Envarsus XR dose adjustments required during the period of DGF.

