9.1. Sample Size Determination

Goal is to analyze 100 subjects total (50 in each group), with a goal to decrease DGF duration to less than 10 days in Envarsus XR group from current mean of 13.9 +/- 7 days with tacrolimus based on the power calculation.

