9.2. Statistical Methods

Continuous data will be compared using Student's t-test or the Wilcoxon Rank Sum test, as appropriate, while categorical data will be analyzed using Fisher's exact test or chi-square test. P values < 0.05 will be considered statistically significant. Kaplan-Meier analyses will be performed to study graft survival if appropriate.

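### Section 9.3 makes dose adjustment the primary analysis and DGF recovery secondary, reversing sections 5.1.1 and 5.1.2 and the basis of the sample size

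*Combined protocol and SAP*

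**What the plan says.** The outcomes are ranked in several places in the combined protocol and SAP.

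- Section 5.1.1: "The primary endpoint of the study will be the interval between first dialysis and last dialysis after kidney transplant (duration of DGF".
- Section 5.1.2: "The secondary endpoint will be number of tacrolimus or Envarsus XR dose adjustments required during the period of DGF".
- Section 4: "Primary Objective: Early recovery from DGF".
- Section 9.1 plans for 50 subjects per group, "with a goal to decrease DGF duration to less than 10 days in Envarsus XR group from current mean of 13.9 +/- 7 days".
- Section 9.3: "Primary analysis include needs for dose adjustment of the Envarsus XR or tacrolimus and secondary analysis include duration of recovery from the DGF".

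Section 9.2 lists tests by type of data without naming an outcome, and adds that "P values < 0.05 will be considered statistically significant". It states neither sidedness nor a rule for more than one outcome.

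**The concern.** Section 9.3 reverses the order in section 5. It is also the only statement in section 9 that assigns an outcome to the primary analysis, so an analyst working from the statistical section would test dose adjustments first. Nothing in the documents says which section prevails.

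Followed literally, 9.3 rests the trial's conclusion on an outcome with no planning figures and makes secondary the outcome on which the trial was sized. If the two results disagree, the text supports presenting either one as the main finding. The trial is open-label (section 7.4), and both dialysis and dose changes are clinicians' decisions (chart-review table in section 8.2.1). The documents do not show which outcome is more open to influence, so the order cannot be settled on that ground and has to be fixed in the text.

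The question arises before the end of the trial. Under section 11.6 the annual DMC reports analyse the primary and secondary outcomes, and an interim analysis is possible. Sections 6.7.1 and 11.5 list efficacy and futility among the grounds for stopping. Those judgements need one agreed primary outcome.

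**Working it through.** **1. The passages side by side**

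| Place | DGF recovery or duration | Dose adjustments |
|---|---|---|
| Section 4 | primary objective | not named |
| Sections 5.1.1, 5.1.2 | primary endpoint | secondary endpoint |
| Section 9.1 | sole basis of the sample size | no figures |
| Section 9.3 | secondary analysis | primary analysis |

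Only 9.3 dissents. The hypothesis in section 3.2 ("less fluctuation of tacrolimus levels requiring less dose adjustment and ultimately early recovery of the DGF") and the expected benefit in section 3.5.3 ("early recovery of DGF, with shorter duration of dialysis treatment after transplant") also point to recovery as the end result.

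The wording differs as well as the order. Section 9.3 speaks of a need for dose adjustment and of duration of recovery. Section 5 defines a count of adjustments and a first-to-last-dialysis interval. Figure 1 lists a further interval, from transplant to recovery, as a separate item.

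**2. Reproducing the sample size for DGF duration**

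Inputs from section 9.1: control mean 13.9 days, +/- 7 read as an SD (it is not labelled), target 10 days (the boundary of the stated goal), 50 per arm. Alpha 0.05 is from section 9.2. Two-sided testing and 80% power are assumptions, because the plan states neither.

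- Difference = 13.9 − 10 = 3.9 days; standardized, 3.9/7 = 0.557 SD.
- Normal approximation: n per arm = 2 × (1.960 + 0.842)² × (7/3.9)² = 50.6, rounded up to 51.
- Power at 50 per arm: 3.9 / (7 × √(2/50)) = 3.9/1.4 = 2.786; 2.786 − 1.960 = 0.826; power 79.6%.
- t-test (noncentral t): power at 50 per arm 78.8%; 80% power needs 51.5, rounded up to 52 per arm.
- One-sided 0.05, t-test: 80% power needs 40.5, rounded up to 41 per arm.

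The stated 50 per arm therefore fits DGF duration, tested two-sided at about 80% power.

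**3. The same exercise for dose adjustments**

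The documents give no expected count, SD or target difference, so no sample size or power can be derived. In SD units, at two-sided 0.05 and 50 per arm:

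- Detectable difference at 80% power = √(2/50) × (1.960 + 0.842) = 0.560 SD by the normal approximation, 0.566 SD by the t-test.
- Power by the t-test at assumed differences: 0.4 SD, 50.8%; 0.3 SD, 31.8%.

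**4. Illustration of the ambiguity**

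If either result could be presented as primary at P < 0.05, the chance of at least one false positive would be 1 − 0.95² = 9.75% for independent outcomes. It is lower with positive correlation: about 9.1% at an assumed correlation of 0.5 and 8.3% at 0.7. The plan does not state this as a rule.

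**The case against.** The strongest reply is that this is a drafting slip. The sections that set the objective, endpoints and sample size all support DGF duration, and the outlier is one sentence under a heading about analysis populations. That reading of intent is very probably right. It does not remove the problem, because the sentence is current, operative text and the only assignment of a primary analysis in section 9.

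Several narrower points are fair:

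- The hypothesis describes a causal chain, which is weaker evidence of ranking than sections 4, 5.1.1, 5.1.2 and 9.1.
- The 0.57 SD detectable difference is a property of 50 per arm for any outcome, and is almost the same as the 0.557 SD planned for DGF duration. It shows no disadvantage in itself; what counts is that nothing was planned for dose adjustments.
- The 0.3 and 0.4 SD cases are assumptions, and the false-positive figure is an illustration.
- Reconciling 9.3 strictly needs only a cross-reference; stating two-sided testing goes further.

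None of these touches the contradiction.

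**Conclusion.** The concern holds. Section 9.3 contradicts sections 5.1.1 and 5.1.2, the primary objective in section 4 and the sample-size basis in section 9.1, and no passage reconciles them. This rests on the text alone. It needs correcting because it decides which result the trial's conclusion rests on.

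The stated 100 subjects are consistent with DGF duration as primary: about 79% power at two-sided 0.05, if +/- 7 is an SD and the difference is 3.9 days. No corresponding statement can be made for dose adjustments. The sample size itself is not in question.

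**What to change.** Replace the second sentence of section 9.3 with text such as:

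> The primary analysis compares DGF duration between arms as defined in section 5.1.1 (interval from first to last dialysis). The secondary analysis compares the number of dose adjustments as defined in section 5.1.2. The trial's conclusion rests on the primary analysis at two-sided 0.05.

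The first two sentences resolve the contradiction and align the wording. The third is a new explicit choice, because the documents do not state sidedness; it agrees with 50 per arm at about 80% power. If the transplant-to-recovery interval in Figure 1 is to be analysed, list it as a separate additional outcome.

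The same amendment could tidy two related mismatches: the study summary in section 1 refers to composite endpoints that are nowhere defined, and the secondary objective in section 4 concerns steady tacrolimus levels, whereas 5.1.2 counts dose adjustments.

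The cost is a wording amendment submitted to the IRB under section 13, with no change to sample size, data collection, patients or procedures. Make it before outcomes are compared by arm, including in DMC reports. If any such comparison has already been made, the amendment should say so.
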